Appendix F: WOUND-Q Instrument

SCALE STRUCTURE

Protocols for interventions to treat and prevent wounds have typically overlooked the patient perspective of outcomes and have focused instead on objective measures. The WOUND-Q is a rigorously developed patient-reported outcome measure that can be used with all types of chronic wounds in any anatomical location. The WOUND-Q measures 4 overarching domains. Each domain includes 2 or more independently functioning scales. Clinicians and researchers are able to administer the subset of scales relevant to their situation.

WOUND CHARACTERISTICS

Three scales measure wound characteristics. The first scale measures how concerned someone is with their chronic wound(s) in the past week. The other two scales measure how bothered people are with drainage and smell.

HEALTH-RELATED QUALITY OF LIFE

Four scales measure health-related quality of life. The first scale measures life impact and the other three measure specific concerns, i.e., how chronic wound(s) affect sleep, psychological, and social function.

EXPERIENCE OF CARE

Four scales measure patients' experience of healthcare. The first scale measures satisfaction with information and the other three measure satisfaction with members of the health care team, i.e., home care nurses, wound team, and office staff in a wound clinic.

WOUND TREATMENT

Confidential Page 70 of 73

Two scales measure common treatments for chronic wounds. One scale measures satisfaction with dressing and the other scale measures satisfaction with the use of a suction device (e.g., vacuum pump device, negative pressure therapy dressing).

Data analysis

WOUND-Q Instrument

- 1. Wound Assessment
- 2. Wound Drainage
- 3. Wound Smell
- 4. Health-Related Quality of Life
- 5. Treatment Dressing

Confidential Page 71 of 73

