Index ulcer measurements	х	х	Х		Х	X	Х	Х	Х	Х	Х	Х	Х	Х	Х	Х	X ^[A]
Assess index ulcer healing > 50%										X							
Index ulcer cleaning	X	х	х		X	X	х	х	х	х	х	х	х	X	х	Х	X ^[A]
Index ulcer debridement	X ^[B]	X ^[B]	X [B]		X ^[B]	X ^[B]	X ^[B]	X [B]	X ^[B]	X ^[B]	X [B]	X [B]	X ^{B]}	X [B]	X [B]	X ^[B]	X [A]
Index ulcer closure assessment			х		Х	X	х	х	х	х	х	х	х	X	х	Х	X _[c]
Assessment of offloading	х	х	х		х	X	Х	х	х	Х	Х	х	Х	Х	х	Х	x
Apply MIRRAGEN™ or FIBRACOL™				X	х	X	X	х	х	X	Х	х	X	X	х		
Apply outer dressing	Х	Х		X	X	X	X	X	X	X	X	Х	X	X	X	X ^[D]	X ^[D]

Confidential Page 24 of 73

[A]: Only assess for reopening of wound; [B]: If required per guidelines; [C]: Confirmation of wound closure; [D] Only if subject is not healed

Confidential Page 25 of 73

^{*}Will be earlier if wound heals before this date or subject is withdrawn from the study.

^{**}Visit windows applicable given that TV1 is at least 14 days from SV1. Subject MUST complete a minimum of a 14-day screening period.

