8.8 WOUND-Q Assessment

The WOUND-Q will be administered to all subjects on SV1, TV3, TV7 and EOS1. This tool will document the impact of the wound on the subject's life and whether the treatment interventions helped to return them to improved functioning.

If a subject discontinues the study, every effort should be made to contact them to complete the WOUND-Q tool on their EOS1 visit.

Further details and the tool itself can be found in Appendix E.

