9.1 Data Analysis

This study consists of primary, secondary and exploratory/tertiary (research) endpoints. Data analysis of study endpoints includes use of validated DFU wound healing measures, quantitative and qualitative analyses, as well as exploratory methodologies. Table 4 below details each study endpoint, corresponding data, and planned analyses.

TABLE 4: ETS WOUND CARE, LLC DFU ENDPOINT DATA ANALYSIS

Endpoint	Endpoint Description	Supporting Study Data	Endpoint Analysis
Primary	Comparison of the proportion of index ulcers "healed" at 12 weeks	Investigator assessment of healing (100% epithelization w/no drainage), measurements of ulcer size using digital imaging and photos	Adjudication panel will determine using photographs of the DFU
	Proportion of Index Ulcers healed at 6 weeks		
	PAR at 6 and 12 weeks	Digital imaging	Mathematical wound area change
	Time to healing within 6 and 12 weeks	Primary endpoint	Mathematical time based on healing
Secondary	Changes in peripheral neuropathy	Semmes Weinstein with vibratory	Mathematical change in scores
	Changes in wound quality of life	WOUND-Q (Quality of life tool)	Mathematical change in scores
	Change in pain levels during trial	NPRS	Mathematical change in scores
	Difference in cellulitis and/or infection at 12 weeks	Observation	Count of positive and negative responses
Exploratory/Tertiary	Changes in tissue perfusion of wound bed and periphery with treatment	SnapshotNIR	Exploratory

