Primary analysis: Proportion of index wounds closed at 12 weeks (group 1 versus group 2) using chi square. Analysis will be adjusted using logistic regression.

Secondary analysis: (1) proportion of Index Wounds closed at 6 weeks (group 1 versus group 2) using chi square; (2) time to heal within 6 and 12 weeks using Kaplan-Meier analysis; (3) PAR at 6 and 12 weeks (group 1 versus group 2) using the Mann-Whitney test; (4) mean difference between groups 1 and 2 of change in weekly peripheral neuropathy score surrounding the DFU using the Semmes Weinstein monofilament with vibratory procedure based on GLM repeated measures; (5) mean difference between groups 1 and 2 of change in WOUND-Q score based on difference between baseline and 12 weeks using t test if data are normal or Kolmogorov–Smirnov test if data are non-normal; and (6) mean difference between groups 1 and 2 of change in weekly wound pain VAS score based on GLM repeated measures.

Control of the familywise error rate (all endpoints) will be achieved through the Hochberg stepup procedure.

Every effort will be made to obtain required data at each scheduled evaluation from all subjects who have been randomized and treated. Subjects who are withdrawn or lost to follow-up will be included in the ITT analysis of primary and secondary endpoints using data imputation methods detailed in the SAP. Sensitivity analysis will also be conducted for the primary endpoint using different imputation algorithms.

10 Adverse Effects and Events (Definitions and Reporting)

The Investigator is responsible for the detection and documentation of any events meeting the criteria and definition of an adverse effect or adverse event (AE), as described in this protocol.

Confidential Page 50 of 73

During the study when there is a safety evaluation, the Investigator or site staff will be responsible for detecting, documenting, and reporting any adverse effect or adverse event, as detailed in this Section of the protocol.

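### Section 9.2 compares arms on raw change in an undefined WOUND-Q score by a t or Kolmogorov–Smirnov test; name one scale and use baseline-adjusted ANCOVA.

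*Combined protocol and SAP*

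**What the plan says.** Section 3 lists change in quality of life by WOUND-Q as a secondary endpoint. Section 9.2, secondary analysis (5), tests the "mean difference between groups 1 and 2 of change in WOUND-Q score based on difference between baseline and 12 weeks". The choice of test is left to the distribution of the data: "using t test if data are normal or Kolmogorov–Smirnov test if data are non-normal". Table 4 in Section 9.1 enters WOUND-Q as one tool, analysed as a change in scores, and names no scale or total. Section 9.2 applies the Hochberg procedure to all endpoints without saying how many hypotheses that covers.

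Appendix F describes four domains and states: "Each domain includes 2 or more independently functioning scales". It adds: "Clinicians and researchers are able to administer the subset of scales relevant to their situation". Its closing list has five entries: wound assessment, drainage, smell, health-related quality of life, and dressing. The fourth entry is itself a domain: "Four scales measure health-related quality of life". The appendix gives no total, scoring rule or combining rule.

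On timing, Section 8.8 says: "The WOUND-Q will be administered to all subjects on SV1, TV3, TV7 and EOS1". The only value before randomization is therefore SV1, and a footnote to the visit schedule says: "Subject MUST complete a minimum of a 14-day screening period".

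Section 9.2 leaves further detail to a formal SAP, due before database lock.

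**The concern.** There are two separate problems.

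**The variable is not defined.** Two analysts following Section 9.2 and Appendix F could test different things: a total of their own making, a mean of the listed parts, or any single scale. A total over the listed parts would mix quality of life with wound smell and dressing satisfaction, although the stated endpoint is quality of life. The trial is open label, and Section 9.2 plans an interim analysis at about 100 subjects to assess outcomes between the groups. If the scale is named only shortly before database lock, it could be named after between-arm results are known.

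**The test is a poor match for the stated comparison.** The stated target is a mean difference in change. A Kolmogorov–Smirnov test can reject because spread or shape differs while the means are equal, and it gives no estimate of a mean difference. The choice between the two tests depends on a normality check for which no criterion is given. Testing raw change also gives up precision that the collected baseline could supply.

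**Working it through.** **Figures in the plan.** No sample size, effect or standard deviation is stated for WOUND-Q, so there is no WOUND-Q figure to reproduce. The only power figure is for the primary endpoint: 100% for 0.70 against 0.35 with 120 per arm at two-sided 0.049. It reproduces (0.9999 with a pooled Z-test, single look) but says nothing about WOUND-Q.

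**Counting the scores (Appendix F).**
- Scales described: 3 + 4 + 4 + 2 = 13.
- Parts listed for use: 5. If the quality-of-life entry is scored as its four scales: 4 + 4 = 8.

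**Counting the Hochberg family (Section 9.2, my count).** Primary 1, closure at 6 weeks 1, time to heal 2, percentage area reduction 2, neuropathy 1, WOUND-Q 1, pain 1: total 9. With five WOUND-Q tests it is 8 + 5 = 13; with eight it is 8 + 8 = 16.

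The smallest Hochberg threshold is α/m at α = 0.05. The detectable difference, in SDs of the analysed variable, is (z for 1 − α/2m + z for 0.80) × √(2/120), with 120 per arm and 80% power:

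| WOUND-Q tests | m | smallest threshold | detectable difference |
|---|---|---|---|
| 1 | 9 | 0.0056 | 0.467 SD |
| 5 | 13 | 0.0038 | 0.482 SD |
| 8 | 16 | 0.0031 | 0.490 SD |

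Entering every score openly therefore costs little power. The problem is that the plan does not say which row applies.

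**Raw change against ANCOVA.** Let σ² be the variance of the score, equal at SV1 and follow-up, and r the correlation between them.
- Raw change: 2σ²(1 − r).
- ANCOVA residual: σ²(1 − r²).
- Ratio: (1 − r²) / [2(1 − r)] = (1 + r)/2.

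The documents give no r, so a range is assumed. The last column is 120 divided by the ratio.

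| assumed r | variance ratio | per-arm size raw change would need to match ANCOVA at 120 |
|---|---|---|
| 0.3 | 0.65 | 185 |
| 0.5 | 0.75 | 160 |
| 0.7 | 0.85 | 141 |

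**Baseline at SV1 or TV1.** SV1 precedes randomization in both arms, so change during the run-in has the same expectation in each arm and cancels from the difference. What remains is noise. Suppose r is 0.1 lower from SV1 than from TV1 (assumed), with the TV1 correlation between 0.4 and 0.8:
- Raw-change variance is multiplied by (1 − r + 0.1)/(1 − r), from 0.7/0.6 = 1.17 to 0.3/0.2 = 1.50.
- ANCOVA variance is multiplied by [1 − (r − 0.1)²]/(1 − r²), from 0.91/0.84 = 1.08 to 0.51/0.36 = 1.42.

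This affects precision only.

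**The case against.** The strongest reply is that scale choice and scoring are ordinary SAP content, and that Section 9.2 promises a SAP with more technical detail. That largely stands: the gap may be closed by a document not yet written. What it does not settle is timing. The only deadline is database lock, which falls after the planned between-group interim in an open-label trial. Section 8.8 also refers to the tool itself, but no questionnaire items appear in the text reviewed, so some scoring material may have been lost when the file was read.

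A second reply is that Hochberg over all endpoints already handles multiplicity. It does if every WOUND-Q score tested enters the family. A reader might infer a type I error of 15–23%, which is what reporting the best of five unadjusted tests at 0.05 would give (1 − 0.95⁵ = 0.226 if independent, about 0.15 at a correlation of 0.7). The documents do not support that reading, because no such unadjusted selection is planned. In simulation under the global null, with the other eight tests independent, family-wise error stays below 5% when all 13 p-values enter. It is about 6 to 7% if the best of five is placed in one slot. What stands is narrower: the number of hypotheses is not fixed.

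A third reply is that ANCOVA is an efficiency preference and that raw change is also unbiased. That is correct for raw change. It does not rescue the Kolmogorov–Smirnov branch, which does not test the mean difference stated.

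**Conclusion.** The point holds as a specification gap and an avoidable loss of precision in one secondary endpoint. The tested WOUND-Q variable is undefined, and its share of the Hochberg family could be one, five or eight tests. ANCOVA on data already collected would cut variance by 15% to 35% relative to raw change, assuming r between 0.7 and 0.3 and equal variances. It would also remove a test that does not address the stated comparison.

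A reader might also infer from the SV1 baseline that the endpoint has no valid value. The documents do not support that. SV1 is a common pre-randomization value, so it adds noise but no bias, and nothing in the text calls a total score invalid. The supported word is undefined, and it rests on the scales, not on the baseline visit.

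**What to change.** In Section 9.2, secondary analysis (5):

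1. Replace the t/Kolmogorov–Smirnov rule with ANCOVA of the follow-up WOUND-Q score on treatment, adjusted for the SV1 value. State that baseline means SV1 for this endpoint, since Section 4.3.1 places baseline procedures at TV1, where WOUND-Q is not given.
2. Designate one quality-of-life scale, of the sponsor's choice, with its scoring rule, as the single WOUND-Q entry in the Hochberg family. Report the other scales descriptively. The sponsor should confirm that the chosen scale is scored separately; Appendix F's list does not show this for the scales within the quality-of-life entry.
3. State which follow-up value is analysed. Section 9.2 says 12 weeks, but the last questionnaire is at EOS1, which Section 4.5 places at Week 13 or earlier.
4. Date the edit before any between-arm review, including the interim at about 100 subjects.

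The cost is wording only: no added visit or questionnaire. The downside is that the other scales lose a formal test. Moving the questionnaire to TV1 is optional and for precision only. It would mean amending the synopsis, Table 1 and Sections 4.5.2, 4.5.3.1 and 8.8 with IRB approval, and subjects already randomized would still have only an SV1 value.

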Appendix G: SnapshotNIR

SnapshotNIR is a near-infrared (NIR), reflectance-based technology that measures tissue oxygen saturation (StO2) in superficial tissue. Using multiple wavelengths of NIR light, SnapshotNIR measures relative amounts of oxygenated and deoxygenated hemoglobin in the microcirculation where oxygen exchange is happening. SnapshotNIR provides users with a tissue oxygenation map that can be used in medical decision making, for tracking and trending oxygenation, and for evaluating tissue viability.

The imaging device is completely non-invasive, eliminating the need for patient contact or injected dyes. Accurately capture diagnostic insight into the availability of oxygenated blood in tissue. SnapshotNIR's actionable data is helping to provide insight for improved decision-making, forging a path in advanced diagnostic-driven wound care throughout the continuum of care.

THE SCIENCE BEHIND SNAPSHOT

Chronic wounds are a health problem with significant reductions in quality of life and can have devastating consequences such as limb amputations and premature death. SnapshotNIR is an imaging device that visualizes and maps tissue oxygen saturation in the capillary network.

Ability to treat nearly all patients, regardless of melanin content for universal peace of mind and care for everybody. Portable and lightweight technology fits easily into your workflow. Both Doctors and nurses can operate it.

Ability to image the actual wound bed and surrounding tissue for a more accurate and precise reading of the wound area.

Confidential Page 72 of 73

Precise visualization of oxygen saturation for faster assessments and healing trajectory predictions. A means to track and document patient progress to improve clinical outcomes and mitigate risks early.

Confidential Page 73 of 73
